### **11.3 Relationship to Investigational Product**

It is a regulatory requirement for investigators to assess relationship to investigational product based on information available. The assessment should be reviewed on receipt of any new information and amended if necessary. “A reasonable possibility” is meant to convey that there are facts/evidence or arguments to suggest a causal relationship.

Facts/evidence or arguments that may support “a reasonable possibility” include, e.g., a temporal relationship, a pharmacologically-predicted event, or positive dechallenge or rechallenge. Confounding factors, such as concomitant medication, a concurrent illness, or relevant medical history, should also be considered.

### **11.4 Laboratory and Other Safety Assessment Abnormalities Reported as AEs and SAEs**

Any abnormal laboratory test results (clinical chemistry, or urinalysis) or other safety assessments (e.g., ECGs, radiological scans, vital signs measurements), including those that worsen from baseline, and felt to be clinically significant in the medical and scientific judgment of the investigator are to be recorded as AEs or SAEs.0, with the exception of hematologic AEs.

However, any clinically significant safety assessments that are associated with the underlying disease or with IC are not to be reported as AEs or SAEs, except for findings judged by the investigator to be more severe than expected for the subject’s condition or death.

Data will be collected for typical disease-related events such as anemia, leucopenia, worsening of thrombocytopenia or infections. All events of possible drug-induced liver injury with hyperbilirubinemia (defined as ALT  $\geq 2.5 \times$  ULN plus bilirubin  $\geq 2 \times$  ULN and/or INR  $> 1.5$  or ALT  $\geq 2.5 \times$  ULN) require reporting as an SAE. Bilirubin fractionation is performed if testing is available. If testing is unavailable and a subject meets the criterion of total bilirubin  $\geq 2 \times$  ULN, then the event is still reported as an SAE. If INR is obtained, include values on the SAE form. INR elevations  $> 1.5$  suggest severe liver injury.

### **11.5 Disease-Related Events and/or Disease-Related Outcomes Not Qualifying as SAEs**

During the study period, the following conditions will not qualify as an AE or SAE provided they are not considered attributable to study medication:

- Cases of disease progression.
- New or worsened cytopenias even if they result in treatment, and/or hospital admissions.
- Serious infections including neutropenic fever/neutropenic sepsis, line-infection, PCP pneumonia, Clostridium difficile infection
- Neutropenic fever/neutropenic sepsis

## 11.6 Pregnancy

Any pregnancy that occurs during study participation must be reported. To ensure subject safety, each pregnancy must be reported to Novartis within 2 weeks of learning of its occurrence. The pregnancy must be followed up to determine outcome (including premature termination) and status of mother and child.

Pregnancy complications and elective terminations for medical reasons must be reported as an AE or SAE. Spontaneous abortions must be reported as an SAE. Any SAE occurring in association with a pregnancy brought to the investigator's attention after the subject has completed the study and considered by the investigator as possibly related to the investigational product, must be promptly reported to Novartis. In addition, the investigator must attempt to collect pregnancy information on any female partners of male study subjects who become pregnant while the subject is enrolled in the study. Pregnancy information must be reported to Novartis as described above.

## 11.7 Time Period and Frequency of Detecting AEs and SAEs

The investigator or site staff is responsible for detecting, documenting and reporting events that meet the definition of an AE or SAE.

AEs will be collected from the start of Investigational Product and through the short-term follow up period. Treatment related AEs will be followed through resolution / stabilization, regardless if this requires clinical monitoring beyond the short-term follow up period. SAEs will be collected over the same time period as stated above for AEs. Any SAEs assessed as related to study participation (e.g., investigational product, protocol mandated procedures, invasive tests, or change in existing therapy) will be recorded from the time a subject consents to participate in the study; all SAEs will be followed through resolution. All SAEs will be reported to Novartis within 24 hours, as indicated.

## Novartis Reporting

All serious adverse events must be reported by facsimile within 24 hours to Novartis at [contact]. Should the designated SAE fax number be non-functional, SAEs should be sent to the designated SAE mailbox: [[contact]](mailto:[contact])

A Novartis SAE report coversheet should be included when reporting any SAE and must include the Novartis study number (CETB115DUS02T), the study title, investigator contact information, and a signature.

### Emergency or after-hours contact information

Contact the page operator at [contact] or toll free at [contact], and ask for the oncologist (cancer doctor) that is on call.

The SAE report should comprise a full written summary, detailing relevant aspects of the adverse events in question. Where applicable, information from relevant hospital case records and autopsy reports should be included. Follow-up information should be forwarded to Novartis within 24 hours.

SAEs brought to the attention of the investigator at any time after cessation of eltrombopag and considered by the investigator to be related or possibly related to eltrombopag must be reported to Novartis if and when they occur. Additionally, in order to fulfill international reporting obligations, SAEs that are related to study participation (e.g., procedures, invasive tests, change from existing therapy) or are related to a concurrent medication will be collected and recorded from the time the subject consents to participate in the study until he/she is discharged.

### **FDA Reporting**

All SAEs that are unexpected (i.e., not in the current PROMACTA™ (Eltrombopag) package inserts or the Investigator Brochures) and associated with use of the study drug must be reported to FDA within 15 calendar days, or within 7 calendar days if the SAE was fatal or life-threatening. Novartis will be responsible for FDA reporting of all necessary SAEs.

### **11.8 Regulatory Reporting Requirements for SAEs**

Prompt notification of SAEs by the investigator to Novartis is essential so that legal obligations and ethical responsibilities towards the safety of subjects are met.

The sponsor-investigator has a legal responsibility to notify both the local regulatory authority and other regulatory agencies about the safety of a product under clinical investigation. The sponsor-investigator will comply with specific regulatory requirements relating to safety reporting to the regulatory authority, /Institutional Review Board (IRB), Novartis, and sub-investigators.

Investigator safety reports are prepared for suspected unexpected serious adverse reactions according to local regulatory requirements and Novartis policy and are forwarded to investigators as necessary.

An investigator who receives an investigator safety report describing an SAE(s) or other specific safety information (e.g., summary or listing of SAEs) from Novartis will file it with the CIB and will notify the IEC /IRB, if appropriate according to local requirements.

## 12.0 STATISTICAL CONSIDERATIONS

The primary goals of this trial are to assess the efficacy and safety of a short course of eltrombopag in elderly AML patients who have no morphological evidence of residual disease on bone marrow biopsy following standard 7+3 induction therapy. The primary endpoint is the proportion of patients with early (by day 24 from the start of induction) platelet recovery to  $\geq 50,000/\mu\text{L}$ . Based on historical data and our own institutional data (unpublished) approximately 60% of patients can be expected to recover platelets to  $\geq 50,000/\mu\text{L}$  by day 24 without additional supportive care beyond platelet transfusions. An increase in the recovery rate to  $\geq 80\%$  would be considered indicative that eltrombopag has significant efficacy in this population.

A two-stage accrual design with a maximum accrual goal of 31 eligible and evaluable patients will be used to test this hypothesis. Twelve eligible patients will be studied initially. If eight or more (67%) have full platelet recovery by day 24 an additional 19 eligible patients will be assessed. If overall 21 or more of the 31 patients have platelet recovery (observed recovery rate  $\geq 68\%$ ) eltrombopag will be accepted for further testing. With this design, there is a  $\geq 56\%$  likelihood of stopping early if eltrombopag's true recovery rate is  $\leq 60\%$ , whereas there is at most a 7% chance if the true recovery rate is  $\geq 80\%$ . The overall likelihood of rejecting eltrombopag if it is not active is  $\geq 81\%$  while there is at most a 9% chance of rejection if it is active.

Adverse events will be graded and categorized using CTCAE version 4.03 criteria. Assuming the trial reaches its maximum accrual goal of 31 eligible patients the likelihood of a particular type and/or grade of toxicity will be estimable using a 95% confidence interval that has a half-width of at most 18%. The likelihood of observing at least one such event is  $\geq 80\%$  even if the underlying risk is little as 5%.

Secondary goals of the trial include estimating the frequency of platelet transfusion independence, the effect of eltrombopag on hemoglobin, and neutrophils, the risk of clinically significant bleeding, clinical efficacy, and time to initiation of post-remission consolidation therapy.

In general categorical data will be summarized as frequency counts and percentages, measured (non-time dependent) data will be summarized as medians and ranges, and “time-to-event” data, such as platelet and neutrophil recovery, and time to CR will be summarized using the Kaplan-Meier method. Exploratory analyses (univariable) will utilize methods such as Fisher's exact test and chi-square tests (categorical data), the Wilcoxon signed-rank, rank-sum, and Jonckheere-Terpstra tests (measured data), and the log rank test and proportional hazards models (time-to-event data). Logistic regression and proportional hazards models will be the primary tools used for any multivariable analyses performed. All tests of statistical significance will be two sided and in general no adjustment to p-values will be made for multiple comparisons due to the exploratory nature of these analyses.

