## 10.0 STUDY ENDPOINTS

### 10.1.1 Primary endpoint

The proportion of patients achieving a platelet count of  $\geq 50,000/\mu\text{L}$  by day 24 of IC on eltrombopag therapy. The treatment response parameters for platelet count recovery for this trial was derived from a cohort of 200 older AML patients (excluding acute promyelocytic leukemia and acute megakaryocytic leukemia) who underwent aggressive 7 + 3 cytarabine-based remission IC at the Cleveland Clinic between 2000 and 2011. The total CR rate in our historical cohort was 41%.

The median time to CR (defined as the time from the start date of IC to the achieving CR per

IWG criteria) was 34 days (range, 14-66). The median time to reach platelet counts  $> 50,000/\mu\text{L}$  was 24 days (range, 17-57) from the start date of IC.

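### Does the roughly 60% no-drug recovery rate behind the single-arm decision rule need a documented, matched source before the rule can stand?

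*Combined protocol and SAP*

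**What the plan says.** Section 12.0 opens by describing the target group as "elderly AML patients who have no morphological evidence of residual disease on bone marrow biopsy following standard 7+3 induction therapy". It then sets the null rate: "Based on historical data and our own institutional data (unpublished) approximately 60% of patients can be expected to recover platelets to" at least 50,000/µL by day 24, with no supportive care beyond platelet transfusions. A rate of 80% or more "would be considered indicative that eltrombopag has significant efficacy in this population".

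Twelve patients are studied first. With eight or more recoveries, 19 more are added, and with 21 or more of 31 "eltrombopag will be accepted for further testing". The plan prints four operating characteristics: early stopping at least 56% likely at a true rate of 60% or less and at most 7% likely at 80% or more; rejection at least 81% likely if the drug is inactive and at most 9% likely if it is active.

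Section 10.1.1 describes an institutional source. The platelet-recovery parameters were "derived from a cohort of 200 older AML patients" given 7+3 between 2000 and 2011, excluding two AML subtypes. The median time to exceed 50,000/µL "was 24 days (range, 17-57) from the start date of IC". On remission it says: "The total CR rate in our historical cohort was 41" per cent. It reports no proportion recovered by day 24.

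Section 3.1 (criterion 4) admits only patients with no morphological disease on the day 14–17 marrow. Section 4.1 confirms a single-arm design.

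**The concern.** Without a control arm, the decision depends wholly on what would have happened without the drug. That figure appears as a round percentage from unpublished data, with nothing to show how many patients it came from or whether they had a clear day 14–17 marrow. The one cohort described is not said to be restricted in that way, and its remission rate of 41% fits an unselected group without proving it. A median of 24 days also suggests, at first sight, that about half the patients had recovered by day 24, and not 60%.

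If 60% is wrong for the patients enrolled, the error rates are wrong too. With a higher true rate, an inactive drug would pass more often than the design implies. With a lower one, the rule would be stricter than intended. What is at stake is the decision to take eltrombopag into further testing.

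**Working it through.** **Inputs (Section 12.0).** Stage 1: n₁ = 12, continue at 8 or more. Stage 2: n₂ = 19. Accept at 21 or more of 31. Null 0.60, target 0.80.

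**Formulas.** With X ~ Bin(12, p) and Y ~ Bin(19, p):

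- P(stop early) = P(X ≤ 7)
- P(accept) = Σ over x = 8 to 12 of P(X = x) · P(Y ≥ 21 − x)

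**Reproducing the plan at p = 0.60.**

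| x | P(X = x) | needed from 19 | P(Y ≥ needed) | product |
|---|---|---|---|---|
| 8 | 0.2128 | 13 | 0.3081 | 0.0656 |
| 9 | 0.1419 | 12 | 0.4878 | 0.0692 |
| 10 | 0.0639 | 11 | 0.6675 | 0.0426 |
| 11 | 0.0174 | 10 | 0.8139 | 0.0142 |
| 12 | 0.0022 | 9 | 0.9115 | 0.0020 |

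The products sum to 0.1936, so rejection is 1 − 0.1936 = 80.6% (printed 81%). Early stopping is 56.2% (printed 56%). At p = 0.80, early stopping is 7.3% (printed 7%), acceptance 91.1% and rejection 8.9% (printed 9%). All four agree to rounding. A false-acceptance figure of 19% is not printed; it is the complement of the 81%.

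**Sensitivity to the null rate, same rule.**

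| True no-drug rate | P(stop early) | P(accept an inactive drug) |
|---|---|---|
| 50% | 80.6% | 2.7% |
| 55% | 69.6% | 8.1% |
| 60% | 56.2% | 19.4% |
| 65% | 41.7% | 37.2% |
| 70% | 27.6% | 58.6% |

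The rule is indeed steep: five points up roughly doubles false acceptance, and five points down more than halves it.

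**Does the 24-day median contradict 60%?** For times in whole days, a median of 24 requires P(T ≤ 23) ≤ 0.50 ≤ P(T ≤ 24). It therefore sets a floor of 50% by day 24 and no ceiling at 50%. If 60% came from the same patients, the share recovering on day 24 itself would be 0.60 − P(T ≤ 23), which is at least 0.60 − 0.50 = 0.10. That is possible. Section 12.0 also names historical data besides the institutional data, so the 200-patient cohort need not be the only source.

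**Which way might 60% err?** Section 10.1.1 does not say whether its median counts patients who never recovered. If it does not, the whole-cohort proportion by day 24 would be lower than the median suggests. Selecting clear day 14–17 marrows plausibly pushes the rate up. The documents give no figure for either effect, so the direction is open.

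**Does the rule depend on a relative gain?** No. Section 12.0 sets an absolute target of 80% or more, and at a true 80% the rule accepts with probability 91.1% whatever the no-drug rate is. It can be made to look weak for a drug that raises 50% to 70% (acceptance 58.6%), but only by replacing the plan's target with a gain of 20 points.

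**The case for a change.** The strongest case for a change is this. The protocol says institutional data exist, the whole decision rests on them, and giving a count and an interval is a small request. Even if 60% had been seen in all 200 patients (an assumption, since no denominator is given), the exact 95% interval would be 53% to 67%, over which false acceptance runs from 5% to 45%. A smaller matched subset would give a wider interval. A result exactly at the cut-off, 21/31, has an exact 95% interval of 49% to 83% (ignoring the stage 1 look), so it could not by itself separate no-drug rates of 50%, 60% and 70%. A benchmark restricted to clear-marrow patients would make the comparison more credible.

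Part of this stands. The documents do not show where the 60% comes from or in whom it was measured, and a reader of the results would want to know.

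The rest does not support a change. The width of the interval around 21/31 comes from the sample of 31, and a better-documented benchmark would not narrow it. The request that the error rates be made conditional is largely met, since Section 12.0 already ties early stopping to a true rate of 60% or less and rejection to an inactive drug. On population, the section names patients without residual disease, then gives 60%, then speaks of this population. Reading 60% as the rate for enrolled patients is natural, though not the only reading. A matched benchmark might also need day-14 marrow results abstracted from 2000–2011 records, and Section 10.1.1 does not say they were captured.

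**Conclusion.** No change to the plan is needed. The 60% is a planning assumption with thin documentation, as is common in single-arm phase II work, and the operating characteristics built on it are right to rounding (56.2%, 7.3%, 80.6% and 8.9% against the printed 56, 7, 81 and 9). The dependence on the null rate is real, with false acceptance of 2.7% at 50% and 58.6% at 70%. But nothing in the documents shows that 60% is wrong, or in which direction, so there is no basis for moving a cut-off. Since the only consequence of passing is further testing, the design is a fair trade-off.

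The gap is one that analysts can fill when they report: give the source, subset and count behind the 60% if available, or call it an assumption; show the acceptance probabilities over 50% to 70%; and set the Kaplan–Meier time to platelet recovery from day 1 of induction, already planned in Sections 10.2 and 12.0, beside the historical 24-day median. This would help interpretation but would alter neither the rule nor its outcome.

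The conclusion rests on independent binomial outcomes with a common recovery rate, on the rule being applied as written, and on the documents alone. The unpublished data could support 60% or undermine it.

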## 7.6 Dosing Delays and Subject Replacement

In case there is an interruption of treatment or if any medication dose is missed this would be captured and subsequently documented on the Dosage Administration Case Report Form (CRF). If the patient's treatment is interrupted, the missed dose will not be replaced. If a patient misses a study dose due to noncompliance (as determined by the treating physician), then the patient would be removed from the study. Subsequently this subject would need to be replaced. If the treatment is interrupted for 1 week due to adverse effect(s) from study medication therapy, then the patient would be removed from the study and the subject(s) would not be replaced.

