## 7.7 Duration of Therapy and Off Study Criteria

Depending on tolerability, eltrombopag can be administered to all assigned study subjects for a total duration of 4 weeks (counted from the first day of eltrombopag administration) unless they meet one of the following criteria for removal from the study:

1. Withdrawal of consent. The patient's desire to withdraw from the study may occur at any time. The investigator should carefully consider whether the patient's withdrawal of consent is due to an adverse event, and if so, record the adverse event as the reason for withdrawal.
2. Violation of the study protocol, including a patient's failure to return for required treatments or assessments or failure on the part of participants with reproductive potential to practice effective birth control or non-compliance.
3. At the treating physician's clinical discretion, if any specific medical or psychosocial changes in patient's condition makes them unacceptable to further participate in the study.
4. If bone marrow biopsy performed to establish remission status (around day 30-45 of remission IC), confirm refractory or persistent disease or if there is leukemic involvement of extramedullary site (biopsy confirmation of skin or organ lesions, central nervous system involvement confirmed either by cerebrospinal fluid analysis or radiological exams) at any time during study.
5. Adverse events, including intolerance of eltrombopag not resolved by dose reduction, life threatening acute hypersensitivity reaction, persistent hepatotoxicity (refer to section 7.4.2), thrombosis/embolism (DVT, PE, stroke, TIA, myocardial infarction) other than central line thrombosis (refer to section 7.5.1) or evidence of disease progression on treatment (myeloid sarcomas). Participants who are removed from the study due to adverse events will be treated and followed according to established medical practice. All pertinent information concerning the outcome of such treatment will be entered in the CRF.

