## 7.8 Duration of Follow Up

All study subjects who achieved a platelet count of 100,000/ $\mu$ L will be followed for a total up to 4 weeks from the stop date of eltrombopag or till the start date of post-remission therapy, whichever occurs earlier, for adverse events and response. The patients who are removed from study for unacceptable adverse events will be followed until that adverse event is resolved or stabilized. All patients will thereafter be followed for 5 years from study enrollment for relapse and survival endpoints as part of institutional standard of care policy for all treated AML patients.

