## 10.2. Secondary endpoints

**1) Kinetics of megakaryocyte recovery:** Parameters to be assessed will include median time to reach platelet count  $\geq 50,000/\mu\text{L}$  and  $\geq 100,000/\mu\text{L}$ , number of days of platelet transfusion, rates of platelet transfusion-independence, median time to reach platelet transfusion-independence and rates of CSBE. The initial time point for assessing different platelet recovery periods will be the first day of remission IC. The number of days of platelet transfusion will be defined as the total number of days in the cycle, beginning with the first day of study drug administration, in which a patient received transfusion. The time to transfusion-independent platelet recovery will be defined as the number of days from the first day of IC until the first of the 5 consecutive days with platelet count equal to or greater than  $50,000/\mu\text{L}$  without a platelet transfusion. For patients who do not achieve platelet recovery before the end of the study, the time to platelet recovery will be censored on the last day of the study. CSBE refers to all bleeding events that require intervention including, but not limited to, transfusional support (red blood cells, platelets and other blood products such as fresh frozen plasma or cryoprecipitate). CSBE will include hematuria, gastrointestinal bleed, retroperitoneal bleed, intra-cranial bleed, uncontrolled epistaxis and muscle or soft tissue hematomas.

**2) Kinetics of granulocytic recovery:** Parameters to be assessed will include the median time to reach absolute neutrophil count (ANC) equal to or greater than  $500/\mu\text{L}$  (first of the five consecutive days with ANC  $\geq 500/\mu\text{L}$ ) and the median time to reach ANC equal to or greater than  $1000/\mu\text{L}$  (first of the five consecutive days with ANC  $\geq 1000/\mu\text{L}$ ) counted from the first day of study drug administration. A neutrophil response will be defined as an absolute increase in ANC of more than  $1000/\mu\text{L}$  within 4 weeks of remission IC.

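### Kaplan-Meier is planned for count recovery and time to CR with no rule for death or refractory leukemia; if these are censored when they occur, the curves overstate success, most of all for CR

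*Combined protocol and SAP*

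**What the plan says.** Section 12.0 (Statistical Considerations) puts time-to-event data, "such as platelet and neutrophil recovery, and time to CR will be summarized using the Kaplan-Meier method". It names no competing-risk method.

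The only censoring rule is in Section 10.2 (Secondary endpoints). For patients without platelet recovery by study end, "the time to platelet recovery will be censored on the last day of the study". It does not say whether that is the individual's last day on study or one day common to all. Neutrophil recovery and time to CR have no censoring rule.

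Patients can leave before reaching these endpoints. Section 7.7 lists as a removal criterion that the remission marrow, around day 30-45 of induction, should "confirm refractory or persistent disease or if there is leukemic involvement of extramedullary site". Section 7.6 covers a one-week interruption for adverse effects: "then the patient would be removed from the study and the subject(s) would not be replaced". Deaths will be known, because Section 7.8 states: "All patients will thereafter be followed for 5 years from study enrollment for relapse and survival endpoints".

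The primary endpoint (Sections 10.1.1 and 12.0) is a simple proportion with platelet recovery by day 24.

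**The concern.** Censoring in Kaplan-Meier assumes that a censored patient would go on to have the event at the same rate as those still at risk. A patient who has died has no further chance of recovery, and one with refractory leukemia has not reached CR with this induction. For time to CR, refractory disease is the opposite outcome. If these patients are dropped from the risk set when they die or leave, their share is passed to the patients who remain. 1-KM then rises above the proportion who truly reach the event, and the median comes too early. A median can even appear when fewer than half ever reach CR.

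CR rate, time to CR and times to platelet recovery are named secondary objectives (Section 2.2). In a single-arm trial, readers are likely to set the curves beside the historical figures in Section 10.1.1: median 34 days to CR and 24 days to platelets above 50,000/µL. The error, if it occurs, favours the drug.

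**Working it through.** **1. The plan's own figures.** With X1 ~ Bin(12, p) and X2 ~ Bin(19, p), early stopping is P(X1 ≤ 7), and overall rejection is P(X1 ≤ 7) + P(X1 ≥ 8, X1 + X2 ≤ 20).
- p = 0.60: 56.2% and 80.6% (stated: at least 56% and 81%).
- p = 0.80: 7.3% and 8.9% (stated: at most 7% and 9%).

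These reproduce to rounding. They use counts by day 24 only, so no Kaplan-Meier estimate enters them.

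**2. The mechanism.** 1-KM(t) = 1 − Π(1 − d_j/n_j), whereas the true proportion is events by t divided by all patients. Suppose 19 of 31 recover (61.3%) and c patients are censored before the first recovery, with the rest followed throughout. Then 1-KM = 19/(31 − c):
- c = 1: 19/30 = 63.3%
- c = 3: 19/28 = 67.9%
- c = 5: 19/26 = 73.1%
- c = 8: 19/23 = 82.6%

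This is the extreme timing. If all non-recoverers are held to a common day after the last recovery, 1-KM is 61.3% for every c.

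**3. Time to CR.** From the documents: median 34 days and CR rate 41% (Section 10.1.1), and removal around days 30-45 (Section 7.7). Assumed: log-normal times with sigma 0.22; deaths in 5-15% of patients, uniform on days 15-55; all other non-responders removed uniformly on days 30-45; every non-responder censored at his or her own date; a second CR rate of 75%. There were 200,000 simulated patients per scenario.

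True proportion at day 45 = CR rate × Φ(ln(45/34)/0.22) = CR rate × Φ(1.27) = CR rate × 0.899.

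| CR rate | True, day 45 | 1-KM, day 45 | True median | KM median |
|---|---|---|---|---|
| 75% | 67% | 79-80% | about day 37.4 | about day 36.4 |
| 41% | 37% | 55-57% | not reached | about day 43.5 |

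The gap is at most 3 points by day 34 and opens after that. With one common late censoring day, 1-KM equals the true column.

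The result depends on how many are censored early. In simulated trials of 31 with 13 CRs (41.9%; assumed normal times, mean 34, SD 7), final 1-KM is about 45-46% if 4 of the 18 non-responders are censored at their own date, and 84-91% if all 18 are.

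**4. Platelet recovery.** Assumed: 31 patients, recoveries from day 17, and deaths or removals spread uniformly over days 17-44 (2,000 simulated trials). The documents give no rate for these events, so 1 to 8 were tried. With 19 recoveries (true 61.3%), 1-KM at day 45 is:
- 1 event: 62.0%
- 3 events: 63.8%
- 5 events: 65.7%
- 8 events: 69.2%

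The excess is 0.7 to 7.9 points, and the median is 0.1 to 1.1 days too early. At day 24 the excess is 0.2 to 1.5 points. It grows when nearly every non-recoverer is censored early: with 25 of 31 recovering and all 6 others censored, 1-KM at day 45 is 92.6% against 80.6%.

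**The case against.** The strongest objection is that the bias is inferred. A reader might take the plan to say that death and refractory removal are censored when they occur, so that the curves are biased as planned. The documents do not say so. The Section 10.2 rule refers to the end of the study, while Sections 7.6 and 7.7 describe individual exits as removal from the study, so a common last day is a fair reading. Under it the platelet curve has no bias. For neutrophils and CR the handling is unspecified. This stands, and the point must be put conditionally.

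A reader might also take the 41% scenario as a forecast for this trial. That rate comes from 200 treated older patients not described as selected on a day-14 marrow, whereas Section 3.1 requires no morphologic leukemia on that marrow. It serves only as an upper illustration of the bias. The 75% is an assumption with no source in the documents.

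Nor do the documents support an effect on the trial's decision. The primary endpoint is binomial, and the refractory-disease marrow falls after day 24. CR, CRp and refractory-disease rates are separate endpoints, so the crude proportions will be visible beside any curve.

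Comparison with the historical 34 days is also unsettled, since the plan does not say how that median was computed. With 41% reaching CR, it cannot be the day by which half of all patients did. It must describe responders only or come from a curve with censoring. No formal comparison is planned.

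What remains is the missing rule. Software censors a patient at the last time at risk unless told otherwise, so the biased reading is the likely default.

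**Conclusion.** The point holds in conditional form. Kaplan-Meier is the stated method, outcomes that rule out the event are built into the protocol, and their handling is not defined. If patients are censored at death or removal, success is overstated.

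The effect is largest for time to CR: roughly 12 to 20 points at day 45 when every non-responder is censored at his or her own date, less if only some are. For platelet recovery it is about 1 to 8 points by day 45 when 19 of 31 recover and exits are spread over time, with about a day or less on the median. It is zero under a common last day. Number, timing and coding of the exits are all assumptions, so the documents cannot fix the size. Only secondary, descriptive results are at stake; the primary endpoint, the two-stage rule and the sample size of 31 stand. The change is worth making because the likely default errs in the drug's favour and the correction is cheap.

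**What to change.** In Section 12.0, for time to platelet recovery, neutrophil recovery, transfusion independence, CR and post-remission therapy, replace Kaplan-Meier with cumulative incidence (Aalen-Johansen). Take death, and refractory or persistent disease or new anti-leukemic therapy, as competing events. Censor only patients who are event-free at their last count.

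An acceptable alternative is to keep patients with a competing event at risk as non-recoverers to one fixed common day, named in advance.

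Reword the end-of-study censoring rule in Section 10.2 to match, and extend it to neutrophil recovery and CR. Report the proportion reaching each endpoint by fixed days and, separately, the median among those who reach it, labelled as such. Keep Kaplan-Meier for overall and disease-free survival.

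The cost is a few sentences and standard software. Deaths and refractory disease are already recorded, so no new data are needed. The downside is that the reported curves will look somewhat less favourable.
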